7.2 Participant Discontinuation/Withdrawal from the Study

A participant may withdraw from the study at any time, at his/her own request or may be withdrawn at any time at the discretion of the Investigator for safety, behavioral, compliance, or administrative reasons.

At the time of discontinuing from the study, if possible, a discontinuation visit will be conducted, as listed in the Schedule of Activities. The Schedule of Activities specifies the data to collect at study discontinuation and follow-up, and any additional evaluations that need to be completed.

If the participant withdraws consent for future involvement in the study, any data collected up to that point may still be used, but no future data can be generated, and any biological samples collected will be destroyed (refer to the Main ICF).

A participant has the right at any time to request destruction of any biological samples taken. The Investigator must document this in the site study records.

7.3 Lost to Follow-Up

A participant will be considered lost to follow-up if he or she repeatedly fails to return for scheduled visits and is unable to be contacted by the study site.

The following actions will be taken if a participant fails to return to the clinic for a required study visit:

- The site will attempt to contact the participant and reschedule the missed visit as soon as possible, counsel the participant on the importance of maintaining the assigned visit schedule, and ascertain if the participant wants to or should continue in the study.

- Before a participant is deemed “lost to follow-up”, the Investigator or designee will make every effort to regain contact with the participant: 1) where possible, make 3 telephone calls; 2) if necessary, send a certified letter (or an equivalent local method) to the participant’s last known mailing address, and 3) if a participant has given the appropriate consent, contact the participant’s general practitioner or caretaker (where allowed by local regulations) for information. These contact attempts should be documented in the participant’s medical record.
- If the participant continues to be unreachable, he/she will be considered to have withdrawn from the study.

8 Study Assessments and Procedures

Study assessments and procedures and their timing are summarized in the Schedule of Activities.

No protocol waivers or exemptions are allowed.

Immediate safety concerns should be discussed with the Sponsor immediately upon occurrence or awareness to determine if the participant should continue or discontinue study intervention.

Adherence to the study design requirements, including those specified in the Schedule of Activities, is essential and required for study conduct.

All screening evaluations must be completed and reviewed to confirm that potential participants meet all eligibility criteria. The Investigator will maintain a screening log to record details of all participants screened, to confirm eligibility, and if applicable, record reasons for screening failure.

Prior to performing any study assessments that are not part of the participant’s routine medical care, the Investigator will obtain written informed consent as specified in [Appendix 2](#).

Procedures conducted as part of the participant’s routine medical care (e.g., blood count) and obtained before signing of the Main ICF may be used for screening or baseline purposes provided the procedures met the protocol-specified criteria and were performed within the time frame defined in the Schedule of Activities.

8.1 Efficacy Assessments and Procedures

Contrast-enhanced computed tomography (CT) imaging of chest/abdomen/pelvis covering the area from the superior extent of the thoracic inlet to well below the symphysis pubis is the first choice of imaging modality. If a participant should not receive iodinated contrast medium, or due to radiation protection reasons, magnetic resonance imaging (MRI) of the same area, using gadolinium enhancement according to local procedure as permitted in conjunction with unenhanced CT of the chest from the thoracic inlet to the inferior costophrenic recess should be done. Regarding MRI for new lesions, in case of doubt, possible new lesions should be followed up on serial MRI before new disease is definitively confirmed. Alternatively, biopsy can be done. The same method should be used per participant throughout the study and preferably the same machines. Brain enhanced MRI (preferably) or enhanced brain CT and/or bone scans should be performed at baseline only for participants suspected to have metastases in these sites. A central

imaging laboratory will be used to read and interpret all CT/MRI/bone scan data; however, treatment decisions will be made by the treating Investigator.

Baseline scans are taken within 28 days prior to treatment. Disease must be measurable with at least 1 uni-dimensionally measurable lesion outside the CNS by RECIST 1.1 assessed by the Investigator. All the scans performed at baseline that are required for RECIST 1.1 assessment need to be repeated at subsequent visits for tumor assessment using the same method, except for brain or bone scans that are negative at baseline. For brain or bone scans that are negative at baseline, no follow-up scans are performed unless there are new symptoms or biochemical changes which suggest PD in these regions. In general, lesions detected at baseline need to be followed using the same imaging methodology and preferably the same imaging equipment at subsequent tumor evaluation visits.

Assessments previously obtained as part of routine clinical care may be used as the baseline assessment if performed within 28 days prior to start of treatment and satisfies tumor assessment requirements as noted in this section.

Participants will be evaluated every 8 weeks within the first 12 months of the participant's first dose, then every 12 weeks through Long-term Follow-up, as scheduled in [Table 1](#).

Confirmation of CR or PR should be performed preferably at the regularly scheduled assessment intervals, but no sooner than 4 weeks after the initial documentation. Confirmation of PR can be confirmed at an assessment later than the next assessment after the initial documentation of PR provided PD does not occur between.

Diagnosis of disease progression based solely on nodal enlargement within 8 weeks of coronavirus vaccination should be made with extreme caution, particularly if in axillary and/or supraclavicular nodes on the ipsilateral side to vaccination and verified with hindsight if possible.

Tumor responses according to RECIST 1.1 will be assessed by the Investigator and an IRC and documented in the eCRF (all measurements should be recorded in metric notation).

8.2 Safety Assessments and Procedures

The safety profile of the study intervention will be assessed through the recording, reporting and analysis of baseline medical conditions, AEs, physical examination findings, vital signs, electrocardiograms (ECGs), and laboratory tests.

Comprehensive assessment of any potential toxicity experienced by each participant will be conducted starting when the participants give informed consent and throughout the study. The Investigator will report any AEs, whether observed by the Investigator or reported by the participant. During Prescreening, only AEs associated with study procedures should be recorded. The reporting period is specified in Section [8.3.1](#).

The safety assessments will be performed according to the Schedule of Activities ([Table 1](#)). Periodic evaluations of the study data will be conducted by the study team to ensure safety and the validity and scientific merit of the study (see Section [8.2.4](#)).

Ongoing events at the 12-week Safety Follow-up Visit should continue to be monitored and documented until resolution or resolution with sequelae. All serious adverse events (SAEs) ongoing at the End-of-Treatment Visit must be monitored and followed up by the Investigator until stabilization or until the outcome is known, unless the participant is documented as “lost to follow-up”. Reasonable attempts to obtain this information must be made and documented. It is also the responsibility of the Investigator to ensure that any necessary additional therapeutic measures and follow-up procedures are performed.

If a liver function test is elevated in an HBV- or HCV-positive participant, HBV deoxyribonucleic acid (DNA) or HCV ribonucleic acid (RNA) must be monitored to exclude the possibility of reactivation of viral hepatitis. In case of viral reactivation, follow the HBV and HCV management guidelines.

8.2.1 Physical Examinations

- Vital signs, physical examinations, and ECOG PS will be conducted at Screening and at subsequent visits as indicated in the Schedule of Activities ([Table 1](#)). These should be documented in the eCRF.
- A complete physical examination will include, at a minimum, assessments of the cardiovascular, respiratory, gastrointestinal, and neurological systems.
- A brief physical examination (at all other scheduled visits other than Screening) will include, at a minimum, assessments of the skin, lungs, cardiovascular system, and abdomen.
- Investigators should pay special attention to clinical signs related to previous serious illnesses.
- General status, such as asthenia or appetite, should be evaluated at baseline. Pre-existing symptoms of underlying conditions and/or signs of infection should be investigated as clinically indicated.
- Abnormal findings are to be re-assessed at subsequent visits.

8.2.2 Vital Signs

- Height (at Screening Visit only) and weight will be measured and recorded.
- Vital signs including body temperature, pulse rate, respiratory rate, and blood pressure will be assessed and recorded in the eCRF.
- Vital signs will be measured in a semi-supine position after 5 minutes rest and will include temperature, systolic and diastolic blood pressure, and pulse and respiratory rate.
- Blood pressure and pulse measurements will be assessed with a completely automated device. Manual techniques will be used only if an automated device is not available.
- Blood pressure and pulse measurements should be preceded by at least 5 minutes of rest for the participant in a quiet setting without distractions (e.g., television, cell phones).

8.2.3 Electrocardiograms

Single 12-lead ECGs will be obtained as outlined in the Schedule of Activities ([Table 1](#)) using an ECG machine that automatically calculates the heart rate and measures PR, QRS, QT, and QTc intervals.

8.2.4 Clinical Safety Laboratory Assessments

- Blood and urine samples will be collected for the clinical laboratory tests listed in [Appendix 6](#) at the time points listed in the Schedule of Activities ([Table 1](#)). All samples should be clearly identified.
- Additional tests may be performed at any time during the study, as determined necessary by the Investigator or required by local regulations.
- The tests will be performed by the local laboratory.
- The Sponsor must receive a list of the local laboratory normal ranges before shipment of study intervention(s). Any changes to the ranges during the study must be forwarded to the Sponsor or designated organization.
- The Investigator must review each laboratory report, document this review, and record any clinically relevant changes occurring during the study in the AE section of the eCRF. The laboratory reports must be filed with the source documents.
- If a participant has a clinically significant abnormal laboratory test value that is not present at baseline, the test should be closely monitored until the test value has returned to the normal range or the Investigator has determined that the abnormality is chronic or stable.
- The report of the results must be retained as a part of the participant's medical record or source documents. Pregnancy testing (serum or highly sensitive urine test, as required by local regulations) will be conducted at monthly intervals during study intervention administration and at the time points specified in the Schedule of Activities ([Table 1](#)), including at the end of relevant systemic exposure of the study intervention.
- HIV testing is not mandatory. History of HIV infection will be collected, if known, as part of the medical history. If a test is performed at any point in Screening or while on study, a site must consent the participant for HIV testing as per local standard guidance.

8.3 Adverse Events and Serious Adverse Events

The definitions of an AE and a SAE are in [Appendix 4](#).

8.3.1 Time Period and Frequency for Collecting Adverse Event and Serious Adverse Event Information

The AE reporting period for safety surveillance begins when the participant is initially included in the study (date of first signature of informed consent/date of first signature of first informed consent) and continues until the 28-day Safety Follow-up Visit, defined as 28 days (\pm 5 days) after the last study intervention administration. After this visit, all SAEs and nonserious

treatment-related AEs should be documented until the last Safety Follow-up Visit, defined as 12 weeks (\pm 2 weeks) after the last study intervention. Ongoing events at the 12-week Safety Follow-up Visit should continue to be monitored and documented until resolution or resolution with sequelae, unless the participant is documented as “lost to follow-up”.

During Prescreening, only AEs associated with study procedures should be recorded.

Any SAE assessed as related to study intervention must be recorded and reported, as indicated in [Appendix 4](#), whenever it occurs, irrespective of the time elapsed since the last administration of study intervention.

The method of recording, evaluating, and assessing causality of AEs (including SAEs) and the procedures for completing and transmitting SAE reports are in [Appendix 4](#).

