		W1	W3	W5	W7	W9	W11	W13	W15	W17			D1	D15	D29	D43	D57	D71	D85	D99	D113
Prior anticancer drug/radiotherapy /procedures for baseline visit	X	X ^d																			Prior anticancer procedures and therapies should at least include prior therapy, prior diagnosis of premalignant lesions and treatments, surgical resection and recurrence, and details on anticancer treatments, treatment duration, and treatment responses. d: Prior therapy collected during Prescreening should be verified and updated (if indicated) at Screening Visit.

Assessments & Procedures	Pre screening	Screening	Intervention Period (\pm 3 days)										End-of-Treatment Visit	Safety Follow-up Visit		Long-term Follow-up	Notes
	Day -28 to Treatment Assignment	V1	V2	V3	V4	V5	V6	V7	V8	V9	Until PD	On the Day of or Within 7 Days of Decision to Discontinue	28 Days (\pm 5 Days) After Last Treatment	12 Weeks (\pm 2 Weeks) After Last Treatment	Every 12 Weeks (\pm 2 Weeks)		
		W1	W3	W5	W7	W9	W11	W13	W15	W17			28 Days (\pm 5 Days) After Last Treatment	12 Weeks (\pm 2 Weeks) After Last Treatment	Every 12 Weeks (\pm 2 Weeks)		
Documentation of concomitant medication and procedures		X	X	X	X	X	X	X	X	X	Q2W	X	X	X ^e	X ^e	e: The 12-week Safety Follow-up and Long-term Follow-up may be conducted via telephone calls or patient chart reviews as necessary unless there is medical necessity requiring.	

Assessments & Procedures	Pre screening	Screening	Intervention Period (± 3 days)										End-of-Treatment Visit	Safety Follow-up Visit		Long-term Follow-up	Notes
	Day -28 to Treatment Assignment	V1	V2	V3	V4	V5	V6	V7	V8	V9	Until PD	On the Day of or Within 7 Days of Decision to Discontinue	28 Days (± 5 Days) After Last Treatment	12 Weeks (± 2 Weeks) After Last Treatment	Every 12 Weeks (± 2 Weeks)		
		W1	W3	W5	W7	W9	W11	W13	W15	W17							
		D1	D15	D29	D43	D57	D71	D85	D99	D113							
Tumor Biopsies/Archival Tissue Collection																	
Tumor tissue collection ^f	X	X ^f		X ^f									X ^f				See Section 8.8. Archival or fresh tumor tissue during Prescreening period is required for HMGA2 testing (see Section 4.1 and 8.8). f: Optional fresh biopsies during Screening, at W3 and End-of-Treatment Visit (excluding bone biopsies) may be tested for CCI [REDACTED] biomarkers (see Section 8.8). Tissue from unscheduled procedures may also be submitted.
Bintrafusp alfa Drug Administration																	
Bintrafusp alfa administration			X	X	X	X	X	X	X	X	Q2W						See Section 4.1 for treatment duration.

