- Drug must not be given to a known pregnant participant (see Appendix 3).
- Use of a prohibited concomitant drug, as defined in Section 6.5.2, where the predefined consequence is withdrawal from the study intervention.

In case of discontinuation from the study intervention:

- The day of End-of-Treatment Visit will correspond to the day of withdrawal (or within 7 days).
- An attempt should be made to perform all assessments scheduled for the End-of-Treatment Visit if possible. If not possible, the most clinically relevant assessments and appropriate eCRFs for the End-of-Treatment Visit should be prioritized as feasible.
- Participants will be asked to continue Safety Follow-up and Survival Follow-up, which includes the collection of data on survival, and subsequent anticancer therapy. After completion of the follow-up period or after the End-of-Treatment Visit, whichever is applicable, the appropriate eCRF section for Study Termination must be completed.
- If the participant is enrolled into a new study or any new therapy post-withdrawal from study intervention, the Safety Follow-up Visit should be scheduled prior to the start of the new treatment irrespective of the 28-day Safety Follow-up period.

The Schedule of Activities specifies the data to collect at study intervention discontinuation and follow-up, and any additional evaluations that need to be completed.

7.1.1 **Temporary Discontinuation**

See Section 6.8 and Section 6.9 for guidance on temporary discontinuation from study intervention.

7.1.2 **Rechallenge**

7.1.2.1 **Reinitiation**

One reinitiating course of treatment at the same dose and schedule and treatment duration up to 24 months is allowed at the discretion of the Investigator and agreement of the Medical Responsible for:

- Participants who are experiencing SD, PR, or CR at the time of discontinuation, and then subsequently develop disease progression after stopping therapy, but prior to the End of the Study.

OR

- Participants who are discontinued due to an AE that are subsequently well managed or resolved after stopping therapy, but prior to the End of the Study.

The participant should reinitiate treatment at the treatment phase visit where they left off according to the Schedule of Activities (Table 1). Participants who reinitiate treatment should stay on study and should be treated and monitored according the Schedule of Activities for the rest of the study.

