9.4.2 Safety Analyses

All safety analyses will be performed on the Safety Analysis population (SAF).

The on-treatment period is defined as the time from the first study intervention administration to the last study intervention administration date + 30 days or the earliest date of subsequent anticancer drug therapy minus 1 day, whichever occurs first, unless otherwise stated.

Data collected after reinitiation of treatment will be summarized according to the specifications in the IAP.

Safety endpoints include AEs, AESIs, clinical laboratory assessments, vital signs, physical examination, and ECOG PS as described in Section 8.2.

The definitions, procedures for recording, evaluating, follow-up, and reporting of AEs are described in [Appendix 4](#).

TEAEs are those events with onset dates occurring during the on-treatment period or if the worsening of an event is during the on-treatment period. The incidence of TEAEs, regardless of attribution, and TEAEs defined as possibly related to bintrafusp alfa will be summarized by MedDRA preferred term and system organ class and described in terms of intensity and relationship to bintrafusp alfa. Any AEs with an onset or worsening date after the on-treatment period will be reported separately.

See Table 12 for safety endpoints and statistical analysis methods. The specifics for safety analysis will be defined in the IAP and finalized before database lock.

Table 12 Safety Endpoints and Statistical Analysis Methods

Endpoint	Statistical Analysis Methods
Primary	Not applicable

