9.7 Time Window

Not applicable.

9.8

Definition of On-treatment Period

The on-treatment period is defined as the time from the first study intervention administration to the last study intervention administration date + 30 days, or the cut-off date or death or the earliest date of subsequent anticancer drug therapy minus 1 day, whichever occurs first, unless otherwise stated.

For participants with treatment ongoing at cut-off date, all data from the first study intervention up to the cut-off date will be considered under the on-treatment period.

Any systemic anticancer therapy, any anticancer surgery and any anticancer radiotherapy as documented in the 'Anti-cancer treatment after discontinuation details', 'Radiotherapy after discontinuation' and 'Surgery after discontinuation' eCRF pages will be considered as subsequent anticancer therapy.

The on-treatment period will include the initial treatment period as well as the reinitiation of treatment period, as applicable. Whether the participant reinitiates treatment (following the rules as outlined in the protocol) or not, the on-treatment period is defined as the time from the first study intervention administration to the last study intervention administration date + 30 days or the earliest date of subsequent anticancer drug (anticancer therapy, anticancer surgery and anticancer radiotherapy) therapy minus 1 day, whichever occurs first, unless otherwise stated.

For immune-related AEs as listed in section 15.2.3.2, an expanded on-treatment period will be used as a default for any analysis, defined as follows:

Time from the first study intervention to the last study intervention date + 90 days, death OR to the earliest date of subsequent anticancer therapy minus 1 day, whichever occurs first, unless otherwise stated.

9.9

Imputation of Missing Data

Unless otherwise specified all data will be evaluated as observed, and no imputation method for missing values will be used.

In all participant data listings, imputed values will be presented, and imputed information will be flagged.

Missing statistics, e.g. when they cannot be calculated, should be presented as 'nd' for 'not determined'. For example, if n = 1, the measure of variability (StD) cannot be computed and should be presented as 'nd'.

The following table for imputation rules for incomplete dates is to be considered:

Table 3 Imputation Rules for Incomplete Dates

Item	Imputation rules

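### AE collection can stop before the 30-day TEAE and 90-day irAE counting windows close, leaving a small, visit-dependent gap in the safety counts

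*Protocol*

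**What the plan says.** Protocol 8.3.1 sets three tiers of collection.

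- All AEs: recording starts at first consent and "continues until the 28-day Safety Follow-up Visit, defined as 28 days" (± 5) after the last dose.
- SAEs and nonserious related AEs: the next sentence runs "After this visit, all SAEs and nonserious" and then "treatment-related AEs should be documented until the last Safety Follow-up Visit, defined as 12 weeks" (± 2 weeks) after the last dose.
- Related SAEs: reportable whenever they occur.

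The counting windows are defined elsewhere. Protocol 9.4.2 ends the on-treatment period at "the last study intervention administration date + 30 days or the earliest date of subsequent anticancer drug therapy minus 1 day", whichever is first. A TEAE is an event that starts or worsens in that period, whatever its attribution. SAP 9.8 keeps the 30 days and adds data cut-off and death as earlier end points. For irAEs, SAP 9.8 substitutes a longer period: "Time from the first study intervention to the last study intervention date + 90 days", again cut short by death or subsequent anticancer therapy. SAP 15.2.3.2 builds the same 90-day limit into the irAE algorithm. That algorithm uses a term list, timing, treatment given, and aetiology or biopsy. It does not use the investigator's relatedness call.

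The 28-day visit also includes haematology, biochemistry, vital signs and ECOG (Protocol Table 1). SAP 15.3 to 15.5 base the corresponding worst-grade, shift and by-visit summaries on the on-treatment period.

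**The concern.** A counting window should not run past the point at which the data are collected. Here it can, on both windows, and it does so even when visits take place on their nominal dates. How much of each window is observed then depends on when the visit was booked.

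Occurrence of TEAEs and treatment-related AEs, including AESIs, is a secondary endpoint. Under SAP 4.1, efficacy, pharmacokinetic, immunogenicity and biomarker analyses are dropped, so safety is the main content left. Moving from tables to listings does not repair this part, because an event that was never recorded appears in neither.

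**Working it through.** The plan states no figure for this point, so the check is window arithmetic. Days are counted from the last dose.

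**Inputs**
- End of all-AE collection: 28 ± 5, so Day 23 to 33, which is 11 permitted days (Protocol 8.3.1 and Table 1).
- End of SAE and related-AE collection: 84 ± 14, so Day 70 to 98, which is 29 permitted days (same places).
- End of TEAE window: Day 30 (Protocol 9.4.2, SAP 9.8).
- End of irAE window: Day 90 (SAP 9.8, 15.2.3.2).

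**Formula:** gap = max(0, end of counting window − day on which collection ends).

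**TEAE window.** Nonserious AEs judged unrelated are the only class affected.
- Visit on Day 23: 30 − 23 = 7 days. This is the maximum, 7/30 = 23% of the window.
- Visit on nominal Day 28: 30 − 28 = 2 days.
- Visit on Day 30 to 33: 0 days.
- There is a gap on 7 of 11 permitted days (Day 23 to 29). If all 11 days are equally likely, the mean is (7+6+5+4+3+2+1)/11 = 28/11 = 2.5 days.

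**irAE window.** Nonserious related AEs and unrelated SAEs that meet the algorithm are affected.
- Contact on Day 70: 90 − 70 = 20 days, the maximum.
- Contact on nominal Day 84: 90 − 84 = 6 days.
- Contact on Day 90 to 98: 0 days.
- There is a gap on 20 of 29 permitted days (Day 70 to 89). On the same equal-weight assumption, the mean is (20+19+…+1)/29 = 210/29 = 7.2 days.

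**The reverse mismatch.** A visit on Day 31, 32 or 33 complies with Protocol 8.3.1 but falls after Day 30. Its laboratory, vital-sign and ECOG results are then outside the on-treatment summaries. Of the 11 permitted days, only Day 30 leaves no uncollected days and also keeps the visit's results inside the window.

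**The case against.** The best defence is that the tiered collection protects what matters. SAEs and related AEs are collected to at least Day 70, and Appendix 4 makes every clinical Grade 4 or 5 AE an SAE. Serious, related and most severe TEAEs are therefore complete to Day 30. That stands, and it is why the effect is small.

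Four stronger readings are tempting, and the documents do not support them.

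- **A 62-day irAE gap (90 − 28).** Most irAEs stay in the second tier. Appendix 4 allows an AE to be called unrelated only if a reasonable alternative explanation is available, while the main irAE route needs no clear other aetiology. A gap of 57 to 67 days remains only for nonserious events judged unrelated that still qualify, through a consistent biopsy or a missing aetiology entry.
- **Protocol 7.1 widens the gap.** It does bring the visit forward: "the Safety Follow-up Visit should be scheduled prior to the start of the new treatment irrespective of the 28-day Safety Follow-up period". But subsequent anticancer drug therapy also closes the counting window, and SAP 9.8 extends this to anticancer surgery and radiotherapy. Visit and window then largely close together. Only a new therapy that is not anticancer treatment would leave a difference.
- **Results from Day 31 to 33 are lost.** They leave the summaries only. Laboratory and vital-sign listings flag values after the on-treatment period, and ECOG is listed at every timepoint.
- **A projected number of missed events.** The documents give no rate for nonserious unrelated AEs, early discontinuation means fewer than the planned 29 participants, and the SAP tabulates participants rather than events.

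Table 1 does mark AE documentation at the 12-week and long-term contacts, but it refers to Section 8.3 for the reporting period, so it does not clearly extend collection. SAP 4.1 may also replace the affected tables with listings. This weakens the reverse mismatch but not the collection gap.

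**Conclusion.** The mismatch is real and no section reconciles it. All-cause TEAEs are under-collected by 2 days at the nominal visit and by up to 7, for nonserious unrelated events only. irAEs are under-collected by 6 days at the nominal contact and by up to 20, for nonserious related events and unrelated SAEs. Related SAEs have no gap. The maximum and nominal figures follow directly from the stated windows. The means of 2.5 and 7.2 days also assume that visits are spread evenly over their permitted days. All figures apply to participants whose counting window is not closed earlier by death, data cut-off or subsequent anticancer therapy.

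This is a stated rule that makes a secondary-endpoint count incomplete to a degree set by visit booking. The amount missed is small and lies mostly among the less important events. It is worth correcting because the correction is simple, not because the safety conclusions are at risk.

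**What to change.** 1. In Protocol 8.3.1, collect all AEs through the later of the Safety Follow-up Visit and Day 30, by telephone if the visit was earlier.
2. In the same section, collect SAEs and nonserious related AEs through the later of the 12-week contact and Day 90.
3. Let either period end sooner where the counting window itself closes at subsequent anticancer therapy.
4. In Protocol 9.4.2 and SAP 9.8, include laboratory, vital-sign and ECOG results from a Safety Follow-up Visit held within its permitted window (to Day 33) in the on-treatment summaries. The TEAE limit stays at Day 30, and the SAP should say that the two limits differ on purpose.

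Steps 1 and 2 bring the two gaps in the working to 0 days. Shortening the irAE window to 84 days would not be enough: contacts on Day 70 to 83, 14 of the 29 permitted days, would still fall short by up to 84 − 70 = 14 days.

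The cost is wording in three sections and a short telephone contact for participants whose visit or contact falls early. A 12-week contact booked on Day 90 to 98, which is already permitted, needs no further call.
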